## 4.2 Scientific rationale for study design

This is a global study designed to continue to investigate the safety and tolerability of tezepelumab versus placebo in severe asthma subjects receiving medium or high dose ICS plus at least one additional asthma controller medication, with or without chronic oral corticosteroids (OCS) and/or other asthma controllers for an additional year. The placebo-controlled study design will help to contextualize endpoints by providing a direct comparator. During the blinded treatment phase (Visits 1-15), half the subjects who were previously assigned to the placebo regimen during the predecessor study will be reassigned to receive tezepelumab, while those who received active drug during the predecessor study will continue on that same regimen. Subjects randomized to placebo in this study serve as comparators to support interpretability of the data collected for subjects randomized to tezepelumab. TSLP has an upstream and central role in the initiation of the immune responses and is expected to have an impact on a broad range of cell types. In the predecessor studies the safety of tezepelumab dosing is being studied over a 52

Tezepelumab - D5180C00018

week and 48 week treatment period in the D5180C00007 and D5180C00009 studies respectively. However, it is important to further understand the safety with continued dosing of tezepelumab for an additional year.

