### 9.2 Sample size determination

The sample size is not based on statistical considerations but will be determined by the number of subjects who complete the double-blind treatment period on investigation product in any of the predecessor studies D5180C00007 or D5180C00009 and meet all study eligibility criteria for the LTE study.

Tezepelumab - D5180C00018

If a pooled analysis will be performed then assuming that 90% of the subjects complete the predecessor studies, and that 90% of those continue into the LTE study, approximately 975 subjects (860 from D5180C00007 and 115 from D5180C00009) are anticipated to enter the LTE study. Furthermore, assuming annual dropout rates during the LTE of CCI (in subjects randomized to tezepelumab) and CCI (in subjects randomized to placebo), total subject years of follow-up of approximately CCI for the “Randomized Placebo” and “Randomized Tezepelumab” treatment groups (as defined in Figure 4 below) are expected in the pooled dataset. Given this exposure, the 95% CIs for an adverse event for which the observed incidence rate is CCI for “Randomized Placebo” and CCI for “Randomized Tezepelumab” using the Rothman-Greenland Method. Confidence intervals based on the data from the individual predecessor studies (non-pooled data) will be wider than described above. Unless otherwise specified, all presentations will be split by predecessor study, and data will not be pooled across the 2 predecessor studies.

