#### 9.4.2 Safety analyses

All safety analyses will be performed on the safety analysis set. Key safety analyses will be repeated using the SAF-LTE analysis set.

The primary objective of the study to evaluate the long-term safety and tolerability of tezepelumab in severe asthma subjects will be assessed through on-treatment AEs (including AESIs, as defined in Section 8.3.8) and SAEs. AEs, AESIs and SAEs will be summarized using exposure adjusted incidence rates (i.e., number of subjects reporting events divided by person-time at risk) to account for the variability in follow-up. CCI

The definition of on-treatment AEs and post-treatment AEs will be defined in the SAP.

The treatment groups for addressing the primary objective will be “Randomized Tezepelumab” and “Randomized Placebo” using the safety analysis set. Supportive analysis of key safety data will be presented for the “Tezepelumab Predecessor+Tezepelumab LTE” and “Placebo Predecessor+Placebo LTE” treatment groups using the SAF-LTE analysis set. Summaries for these 4 treatment groups will be provided overall (Week 0 to Week 104) and by time period

Tezepelumab - D5180C00018

(Week 0 to Week 52/48, Week 52/48 to Week 104). An additional summary of key safety data will be provided for the “Placebo Predecessor+Tezepelumab LTE” treatment group for the SAF-LTE analysis set by time period (Week 0 to Week 52/48, Week 52/48 to Week 104) only.

CCI The “All Tezepelumab” treatment group may additionally be used to report AESIs (rare events) for the safety analysis set. In addition, AESIs may be assessed using the pooled data across the 2 studies.

Laboratory data will be summarized by presenting shift tables using normal ranges (baseline in predecessor study to most extreme post-baseline value) and by presenting summary statistics of observed and change from baseline values (means, medians, quartiles, ranges). The incidence of clinically notable laboratory abnormalities will be summarized.

Further details on additional analyses and presentation of safety data will be provided in the SAP.

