4.5 Safety and tolerability

4.5.1 Adverse events

AEs will be summarised separately for the on-treatment and on-study periods as defined in Section 3.2.2 unless stated otherwise. All AE summaries will be presented by analysis set and treatment groups as follows:

- SAF (Randomised Tezepelumab and Randomised Placebo), overall only
- SAF-LTE (Tezepelumab Predecessor+Tezepelumab LTE and Placebo Predecessor+Placebo LTE), overall and by time period
- SAF-LTE (Placebo Predecessor+Tezepelumab LTE), predecessor and LTE periods

All AEs will be listed for the SAF-LTE analysis set. AEs occurring during the screening/runin period or occurring post-treatment will be highlighted with an asterisk in the listing, but
not summarised separately. In addition, for subjects with a delay between the predecessor
study EOT visit and LTE study Visit 1, a listing of AEs starting more than 33 days after the
last dose of IP in the predecessor study but prior to Visit 1 in the LTE study will be provided.
A further listing of AEs occurring between the LTE study Visit 1 and the date of first dose in
the LTE study will be provided for those subjects who do not receive their first dose of IP in
the LTE study at Visit 1 of the LTE study. Information related to the outcome of any
pregnancies will also be listed for the SAF-LTE analysis set.

For each of the summaries below, the following will be included:

- Number and percentage of subjects reporting at least one AE.
- Exposure adjusted incidence rates (as defined in Section 3.2.2) per 100 subject-years

An overall summary table will be produced showing the following categories: any AEs, serious adverse events (SAEs), AEs with a fatal outcome, and AEs leading to discontinuation of IP (DAEs).

All AEs will be summarised by system organ class (SOC) and preferred term (PT) assigned to the event using the MedDRA dictionary. For each PT, for the number of subjects reporting at least one occurrence of the event, subjects with multiple occurrences of the same PT will only be counted once for the calculation of incidence rates.

Similar summaries by SOC and PT will also be presented for:

- SAEs
- Fatal AEs
- DAEs on-treatment period only

- DAEs causally related to IP on-treatment period only
- SAEs leading to discontinuation of IP on-treatment period only
- Each AESI category separately on-treatment period only

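### SAP 4.5.1 reports the primary adverse-event rates as point estimates only, with no 95% confidence interval and no tezepelumab–placebo difference

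*SAP*

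**What the plan says.** SAP 4.5.1 sets out what each AE summary contains. It has two items: the number and percentage of subjects with an event, and "Exposure adjusted incidence rates (as defined in Section 3.2.2) per 100 subject-years". SAP 3.2.2 defines that rate as subjects with an event over total exposure, each subject counting once, and gives no interval. No blacked-out text is visible at the list in 4.5.1.

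Protocol 9.2 says of the study size: "The sample size is not based on statistical considerations but will be determined by the number of subjects who complete" the predecessor treatment periods and meet the entry criteria. It then describes precision under a condition, "If a pooled analysis will be performed then assuming that 90% of the subjects complete the predecessor studies", and continues: "Given this exposure, the 95% CIs for an adverse event for which the observed incidence rate is" (values blacked out), naming the Rothman-Greenland method. It adds: "Confidence intervals based on the data from the individual predecessor studies (non-pooled data) will be wider than described above". SAP 1.3 repeats this. Both documents split presentations by predecessor study unless stated otherwise. For special-interest events, Protocol 9.4.2 allows an exception: "AESIs may be assessed using the pooled data across the 2 studies".

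On the role of placebo, Protocol 4.2 says: "Subjects randomized to placebo in this study serve as comparators to support interpretability of the data collected for subjects randomized to tezepelumab". For the secondary endpoint, SAP 4.6.1 fits a negative binomial model and reports a treatment effect with a 95% CI. Protocol 9.1 and SAP 4.1.1 rule out formal hypothesis tests for the whole study.

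**The concern.** The planning text describes precision through confidence intervals on AE rates, but the AE output lists none. The lack of formal testing does not explain this, because the exacerbation rate is also untested and still receives an estimate with an interval.

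The placebo arm is kept for two years so that the tezepelumab data can be interpreted against it. With two bare rates side by side, a reader cannot tell whether similar values mean little difference or little information. This matters most for uncommon events and for subjects from D5180C00009, a small group that is reported on its own.

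**Working it through.** **1. Specifications side by side.**

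| Item | Estimate | 95% CI | Between-group contrast |
|---|---|---|---|
| Planning text (Protocol 9.2, SAP 1.3) | AE rate per group, pooled | yes | no |
| Primary output (SAP 4.5.1) | AE rate per group, by study | not listed | not listed |
| Secondary output (SAP 4.6.1) | exacerbation rate | yes | yes |

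**2. The plan's own figures.** 860 + 115 = 975, as stated. The planning CIs cannot be reproduced, because the dropout rates, subject-years and event rates are blacked out. What follows is an illustration on assumptions.

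**3. Implied predecessor totals.** Completion and rollover are each 90%, so 0.9 × 0.9 = 0.81. Then 860/0.81 ≈ 1,062 and 115/0.81 ≈ 142. The documents do not give these totals.

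**4. Subject-years.** Assumptions: 1:1 predecessor allocation (which yields the stated 3:1 ratio in the extension); mean predecessor follow-up 95% of planned; 10% annual dropout in the extension, so 95% mean follow-up there; exposure not stopped at the first event. Randomised Placebo time ends at the switch to tezepelumab.

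- D5180C00007 tezepelumab: 530.9 × 0.95 + 430 × 0.95 = 504.3 + 408.5 ≈ 913
- D5180C00007 placebo: 504.3 + 215 × 0.95 = 504.3 + 204.3 ≈ 709
- D5180C00009 tezepelumab: 71.0 × 0.95 × 48/52 + 57.5 × 0.95 × 56/52 = 62.2 + 58.8 ≈ 121
- D5180C00009 placebo: 62.2 + 28.75 × 0.95 × 56/52 = 62.2 + 29.4 ≈ 92

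With extension dropout of 5% to 20%, D5180C00007 moves from 924 vs 714 to 891 vs 698, and D5180C00009 from 123 vs 92 to 118 vs 90. The redacted dropout rates hardly matter within that range.

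**5. Intervals when the true rates are equal.** Events = rate × subject-years / 100. Ratio CI = exp(±1.96 × √(1/e₁ + 1/e₀)). Difference half-width per 100 subject-years = 1.96 × 100 × √(e₁/PY₁² + e₀/PY₀²).

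| Rate per 100 | D5180C00007 events | Ratio CI | Difference | D5180C00009 events | Ratio CI | Difference |
|---|---|---|---|---|---|---|
| 1 | 9.1 / 7.1 | 0.37–2.67 | ±0.98 | 1.2 / 0.9 | 0.07–15.1 | ±2.71 |
| 5 | 45.6 / 35.4 | 0.64–1.55 | ±2.19 | 6.1 / 4.6 | 0.30–3.37 | ±6.07 |
| 10 | 91.3 / 70.9 | 0.73–1.36 | ±3.10 | 12.1 / 9.2 | 0.42–2.36 | ±8.58 |

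The D5180C00009 row at 1 per 100 is only indicative, because about one event per arm is too few for this approximation.

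**6. Pooled against non-pooled width (log scale).** √(975/860) = 1.06 and √(975/115) = 2.91. The pooled planning CIs describe D5180C00007 well and D5180C00009 poorly.

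**7. Limits on the choice of method.**

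- *Zero events.* The log interval above is undefined at zero. With 1.21 and 0.92 expected events, the chance that at least one arm has none is 1 − (1 − e^−1.21)(1 − e^−0.92) ≈ 0.58.
- *Period mix.* In D5180C00007, predecessor time is 504.3/708.6 ≈ 71% of placebo exposure but 504.3/912.8 ≈ 55% of tezepelumab exposure. A crude difference would mix treatment with period.
- *Any AE.* Each subject counts once over exposure that continues after the event. Protocol 2.2 reports that about 66% of Phase 2 subjects had an event. With a proportion p affected, the count varies as np(1 − p) and not as np, so at p = 0.66 a Poisson-type interval would be about 1/√0.34 ≈ 1.7 times too wide.

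**The case against.** The best case for the plan is that descriptive AE reporting is its declared design. The primary objective speaks of evaluating tezepelumab; only the secondary objective names a comparison with placebo. Nothing is formally tested, and no readable text promises an AE interval, so the SAP contradicts nothing visible. Both documents also disclose that non-pooled intervals will be wider. Counts stand beside the rates and exposure is tabulated, so a reader could work out an interval.

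Much of this stands. It shows an omission and not a contradiction. It does not show that the omission is harmless. The synopsis rationale sets long-term safety against placebo, and Protocol 9.4.2 names the two primary groups for this objective. A home-made interval from the published counts would also run into every problem in step 7 of the working.

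A reader might infer more than the documents support:

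- *That the study size is justified by CI width.* It rests on rollover; the CIs only illustrate precision.
- *That no precision is stated anywhere.* It is stated for the pooled case, with values blacked out. What is missing is an interval in the planned AE output.
- *That the protocol itself excludes intervals or contrasts.* Text directly after the rate sentence is blacked out in the synopsis and in 9.4.2, so the protocol's silence cannot be shown.
- *That placebo is never formally compared.* It is, for exacerbations.
- *That not pooling the special-interest events is a deviation.* Protocol 9.4.2 makes pooling optional.
- *That every AE rate needs an interval.* That would fill each preferred-term and subgroup table for little gain.

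**Conclusion.** The point holds for the readable SAP. Following the list in 4.5.1 gives a primary safety result with no interval and no tezepelumab–placebo estimate, whereas the planning text uses such intervals and the secondary endpoint receives both. This should be fixed. It does not undermine the design or the size of the study.

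The consequence is moderate in D5180C00007 and large in D5180C00009, where at 5 events per 100 subject-years equal observed rates leave room for a threefold difference either way. These sizes rest on back-calculated predecessor totals, 1:1 predecessor allocation and about 95% follow-up. They vary little with extension dropout of 5% to 20% but strongly with the event rate.

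**What to change.** In SAP 4.5.1 and Table 10, for the on-treatment comparison of Randomised Tezepelumab with Randomised Placebo in the SAF, by predecessor study, and only for any AE, SAE, DAE, fatal AE and each AESI category:

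- Add a 95% CI to each exposure-adjusted rate, by a method valid at zero or few events, such as exact Poisson.
- Add the tezepelumab-minus-placebo rate difference with a 95% CI, such as a score-type interval, stratified by period (predecessor, LTE).
- For any AE, use a subject-level bootstrap, or state that the Poisson-type interval is approximate.
- Label all these intervals descriptive, without multiplicity control.

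In Protocol 9.2 and SAP 1.3, state the precision expected for the non-pooled analysis that is actually planned. A study-stratified pooled AESI estimate is optional under Protocol 9.4.2.

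The cost is SAP wording and modest programming, with no new data. SAP 4.5.1 now shows the SAF overall only, so the stratified difference also needs SAF counts and exposure by period, for which SAP 3.1.5.1 already has definitions. The main downside is a set of descriptive intervals that must not be read as tests.

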### **On-Site Randomization, Treatment and Follow-up for subjects that rolled over from D5180C00007 or D5180C00009**

**Please NOTE:** If a subject is unable to attend an onsite EOT visit in NAVIGATOR or SOURCE due to the COVID-19 pandemic please refer to [Appendix H](#) for further guidance on roll over and participation into the DESTINATION study.

The study will consist of a screening/randomization visit which will be the same day as the End of Treatment (EOT) visit from the predecessor studies D5180C00007 (Week 52) or D5180C00009 (Week 48). The first dose of IP will be administered the same day. During the screening/randomization visit, subjects must undergo all assessments per [Table 1](#). Prior to randomization the subjects must meet all inclusion/exclusion criteria for LTE study. If a subject does not meet all inclusion criteria or meets any exclusion criteria as per [5.1](#) and section [5.2](#), the subject will be screen failed and would then complete the safety follow-up portion of the predecessor study. Further details are specified in section [5.4](#).

A treatment period duration of 52 weeks for subjects who previously completed study D5180C00007 or 56 weeks for subjects who previously completed the D5180C00009 will follow. The last dose of IP will be administered at Week 100. EOT visit will be conducted at Week 104. IP will not be administered at week 104. This is followed by a 12-week follow-up period which includes 2 follow-up visits (Visit 16 and Visit 17).

Tezepelumab - D5180C00018

Subjects who prematurely discontinue IP during the LTE study will be encouraged to undergo all study visits/procedures for the full treatment period. Further information is provided in section 7.1.1. Any new treatments that are initiated will be recorded in the electronic case report form (eCRF).

CCI

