### 5.3 Lifestyle restrictions

Subjects must abstain from donating blood and plasma from the time of informed consent, and for 16 weeks (5 half-lives) after last dose of IP.

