#### 8.4.2.2 Paternal exposure

Pregnancy of the subject's partners will not be considered an AE. However, the outcome of all pregnancies (spontaneous miscarriage, elective termination, ectopic pregnancy, normal birth, or congenital anomaly) should be followed up and documented in the pregnancy report form for conceptions occurring from the date of the first administration of IP until 16 weeks (5 half-lives) after the last administration of IP. Consent from the partner must be obtained before the pregnancy report form is completed.

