3.2.2 Adverse events – general

Adverse events (AEs) experienced by any subject at any time during the entire study will be coded using the latest version of the Medical Dictionary for Regulatory Activities (MedDRA) at the time of the primary database lock. This version of MedDRA will also be used during the final database lock.

AEs will be categorised for analysis according to their onset date into the following study periods for the SAF and SAF-LTE analysis sets:

- AEs occurring during screening/run-in period: date of Visit 1 in the predecessor study ≤
 AE onset date < date of first dose of IP in the predecessor study
- AEs occurring during on-treatment period: date of first dose of IP \leq AE onset date \leq minimum (date of last dose of IP + 33 days, date of death, date of study withdrawal)
- AEs occurring during post-treatment/follow-up period (for subjects still being followed up then): date of last dose of IP + 33 days < AE onset date ≤ study completion or withdrawal date
- AEs occurring during on-study period: date of first dose of IP ≤ AE onset date ≤ study completion or withdrawal date.

In addition, AEs will be further categorised for analysis for the on-treatment and on-study periods by the predecessor and LTE time periods as defined in Section 3.1.5.1.

If the AE has a completely missing (and unresolvable) onset date, then the AE will be assumed to have occurred during the on-treatment period, unless the end date indicates unambiguously that the AE resolved before treatment started. If the AE has a partially missing (and unresolvable) onset date, then the AE will also be assumed to have occurred during the on-treatment period, unless either the end date indicates unambiguously that the AE resolved before treatment started, or the partial onset date is in the month/year prior to start of treatment.

For each treatment group, exposure adjusted incidence rates will be defined as the number of subjects reporting adverse events divided by total exposure duration for that treatment group.

For individual subjects, exposure duration (days) for each time period is derived using the start date and end date defined for the on-treatment and on-study period in Section 3.1.5.1. The total exposure duration (years) for a treatment group will be derived as the sum of the individual subject exposure duration (days) for that treatment group and divided by 365.25.

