8.1.6 Severe infections (as defined in the protocol)

Severe infections will use an investigator-driven definition, i.e. will be directly determined from what is entered on the eCRF.

A subject will be considered to have this AESI if the subject has at least one preferred term with AE onset date during the relevant study period for analysis, which satisfies the following:

"AE Category" on Adverse Events eCRF page marked as "Severe Infection", and one or more of the following:

- AE is serious ("Serious" on Adverse Events eCRF page marked as "Yes"), or
- AE required treatment with systemic antiviral medications, intravenous antibiotics or medications for Helminth parasitic infection, or
- AE resulted in permanent discontinuation of study drug ("Action taken, investigational product" on Adverse Events eCRF page marked as "Drug permanently discontinued").

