8.1.8 Opportunistic infections

Opportunistic infections will be defined using a pre-specified list of preferred terms (AZ defined SMQ).

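### The AESI category tables by SOC and PT stop at last dose + 33 days, so they give no on-study category rate that includes the collected follow-up

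*SAP*

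**What the plan says.** SAP 4.5.1 opens with a default: AE summaries are produced for the on-treatment and the on-study period unless stated otherwise, with exposure-adjusted incidence rates per 100 subject-years. All AEs by SOC and PT, SAEs and fatal AEs carry no exception. The AESI bullet does: "Each AESI category separately on-treatment period only". The All Tezepelumab AESI summaries and the breakdowns of injection site reactions are also on-treatment.

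SAP 3.2.2 ends the on-treatment period for AEs at the earliest of "date of last dose of IP + 33 days, date of death, date of study withdrawal". The on-study period runs to study completion or withdrawal.

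Protocol 8.3.2 has AEs collected through follow-up. SAP 4.5.1 marks post-treatment AEs with an asterisk in the SAF-LTE listing and gives them no summary of their own.

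Three related items are less clear or differ:
- The AESI-by-causality summary in 4.5.1 states no period.
- The repeat of the AESI summaries as occurrence rates states no period either.
- In Table 10 (SAP 8.4), the AESI rows by SOC/PT and by occurrence rate are marked on-treatment only in the All Teze column. The other columns carry a plain tick.

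**The concern.** Long-term safety is the primary objective, and AESIs are the events the protocol singles out within it. The follow-up visits run to the point the protocol equates with five half-lives, and AEs are collected throughout. SAP 4.5.1 uses that time in the on-study tables of AEs, SAEs and fatal AEs, but not in the table that groups events into AESI categories.

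Some categories cannot be recovered from the general tables. SAP 8.1.6 says "Severe infections will use an investigator-driven definition", so membership depends on eCRF flags that a SOC/PT table does not show. At stake is a category-level result for the period when drug is still present but declining. For some AESI categories the plan would not otherwise clearly produce one.

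**Working it through.** **Inputs**
- Half-life: Protocol 5.3, "for 16 weeks (5 half-lives) after last dose of IP". Protocol 8.4.2.2 agrees: "until 16 weeks (5 half-lives) after the last administration of IP".
- Last planned dose: Protocol 4.1, "The last dose of IP will be administered at Week 100".
- End of follow-up: Visit 17, Week 116 (Protocol 4.1 and Table 1).
- Target days: SAP Table 3 puts Week 100 at day 701, Week 104 at day 729 and Week 116 at day 813.
- End of on-treatment: last dose + 33 days (SAP 3.2.2).

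**The plan's own figure.** Week 100 + 16 weeks = Week 116, and 813 − 701 = 112 days = 16 × 7. Follow-up therefore ends at the stated five half-lives.

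**Drug remaining.** Half-life = 112 / 5 = 22.4 days. With first-order decay, the fraction remaining t days after the last dose is 0.5^(t/22.4):
- day 28 (Week 104): 42%
- day 33 (end of on-treatment; 33 / 22.4 = 1.47 half-lives): 36%
- day 70 (Week 110): 11.5%
- day 112 (Week 116): 3.1%

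If 16 weeks is a rounded figure and the half-life lies between 20 and 26 days (an assumed range), 32% to 42% remains at day 33.

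**Time left out, for a completer with the 12-week follow-up.** On-treatment ends on day 701 + 33 = 734. Days left out: 813 − 734 = 79. That is 79 / 112 = 71% of the time after the last dose, and 79 / 813 = 9.7% of on-study time.

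**Subjects who enter the redacted period.** SAP 3.1.5.1 ends their LTE on-study period at Week 104 (day 729), which is before day 734. In LTE-period tables an on-study version adds little or nothing for them.

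**Can other on-study tables stand in for the category table?**
- Severe infection needs an eCRF category plus seriousness, specified treatment or permanent discontinuation (SAP 8.1.6). The serious ones appear in the on-study SAE table, but as separate terms.
- Helminth infection needs a linked eCRF page (SAP 8.1.5).
- Opportunistic infection and Guillain-Barre syndrome are groups of terms (SAP 8.1.8, 8.1.9). Adding PT rows counts a subject with two terms twice.
- Adrenal crisis, for D5180C00009 only, uses high-level and lower-level terms (SAP 8.1.10), and a SOC/PT table does not show these.
- Immune complex disease is a single PT (SAP 8.1.2), so the on-study PT table covers it.
- Malignancy is also summarised as adjudicated events, with no period restriction (SAP 4.5.1).
- Anaphylactic and injection site reactions are tied to the injection, so later follow-up adds little.

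**The case against.** The strongest reply is that the window was chosen on purpose and coverage is better than the bullet suggests.

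- **Prespecified window.** Protocol 9.4.2 assesses the primary objective on on-treatment AEs, AESIs included, and 33 days equals the 28-day dosing interval plus the 5-day visit window. This stands as a reason to keep on-treatment as the main display. It does not explain why AEs and SAEs, under the same protocol sentence, get an on-study table and AESI categories do not.
- **Other summaries.** Read literally, the default in 4.5.1 makes the AESI-by-causality summary due on-study as well, since it carries no restriction. This stands, and it limits the claim to the SOC/PT category tables. It also means an on-study causality table could appear with no matching on-study category table.
- **Redaction.** The AE block of Table 10 also points to Section 4.7.2, which is blacked out, and Protocol 9.4.2 has redacted text. AESIs in the redacted period may be covered there. The point therefore concerns only what 4.5.1 visibly specifies.
- **Rates.** A reader might infer that stopping at day 33 understates risk. The documents do not support that. Events and exposure time are cut together, so the rate would rise only if the event rate were higher after day 33 than before it, and drug levels are falling then.
- **Data maturity.** The primary lock follows the last subject's Week 104 (Protocol 9.4), so Week 116 follow-up may be incomplete. This stands, and it applies equally to the on-study AE and SAE tables.

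**Conclusion.** The point holds in a limited form. SAP 4.5.1 leaves the AESI category tables by SOC and PT without an on-study version, although the general AE, SAE and fatal-AE tables have one. The cut falls where about 36% of drug remains, and it leaves out up to 79 days for completers who have the 12-week follow-up. The practical gap is in severe, helminth and opportunistic infections, Guillain-Barre syndrome and adrenal crisis.

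A reader might go further and conclude that AESIs in follow-up receive no rate at all. That is not so: they enter the on-study SOC/PT rates, immune complex disease is covered by its one PT, and adjudicated malignancy has no period limit. Nor does the 79 days apply to everyone.

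The drug-remaining figures assume that 16 weeks equals five half-lives, that elimination is first-order, and that subcutaneous absorption can be ignored. The direction of any change in the rates is unknown. This is a cheap improvement to reporting. It is not an error in the primary safety analysis.

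**What to change.** - In SAP 4.5.1, also summarise the non-acute AESI categories for the on-study period, with incidence and occurrence rates. Label this supportive and keep on-treatment as the main display.
- State the period for the AESI-by-causality summary and for the occurrence-rate repeat.
- Align the existing AESI rows of Table 10 with that text. No new row is needed.

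The data and category definitions already exist, so the cost is a rerun of existing tables. The downside is that on-study rates mix time on and off drug, especially for subjects who stop treatment early and stay in follow-up, and that follow-up may be incomplete at the primary lock. A footnote should say both.
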